To address the gaps in cervical cancer screening, the ELEVATE project is developing a screening strategy to make cervical screening more accessible to hard-to-reach women. This strategy will include the introduction of a new on-site HPV self-sampling screening tool and a portable testing device, able to detect the presence of HPV and cancer biomarker proteins. This portable, low-cost, on-site HPV testing tool will allow to streamline follow-up care for women at risk of developing cervical cancer.

2. Background

Even though preventive approaches and strategies are different in European and Latin American contexts, coverage levels are not sufficient in all countries. In Ecuador, coverage at national level ranges between 9 to 20% (9). In Brazil, the coverage rate for the cervical cancer-screening program (opportunistic) is estimated to be below 70% (10). In Portugal and Belgium, screening coverages reaches 70.7% and 55%, respectively (11-14). This means that in all countries a significant part of the eligible female population is not screened regularly for cervical cancer (15,16). Those women, called "hard-to-reach women", are defined as women who are eligible for cervical cancer screening and who, for specific reasons to be further clarified in this study, do not participate in screening and consequently are at higher risk for cervical cancer. They are often from minority groups or living in isolated areas and face multiple barriers in accessing preventive care.

To help define and characterize the hard-to-reach populations who do not attend cervical cancer screening in the study countries, a comprehensive literature review was conducted in each study country focusing on prevalence of HPV and cervical cancer, cervical cancer screening uptake, associated factors, current screening strategies and, in addition, an analysis of official national databases was conducted. Overall, major factors associated with low participation in cervical cancer screening found in the four countries included lower education and low income, as well as poor health literacy and lack of knowledge about cervical cancer. In Belgium and Portugal, evidence also shows that older age, being unemployed and being migrant are negatively associated with screening participation. Distance to healthcare facilities and living in remote areas were factors addressed in literature from Brazil and Ecuador. In Portugal non-regular appointments with GPs and non-adherence to mammography was associated with low participation in screening. Other barriers to screening were identified in Belgium and Ecuador's literature reviews and included fear of the test and its result, negative past experiences in healthcare services, lack of time and other life priorities. These results allowed to identify specific hard-to-reach populations for cervical cancer screening in the four countries.

To further understand barriers and facilitators to participation in cervical screening and to explore alternative strategies to promote screening among hard-to-reach populations, a focus group study has been conducted in each study country. Building on the results of these studies, a self-sampling HPV testing intervention will be launched in hard-to-reach communities in these four countries: Belgium, Brazil, Portugal and Ecuador.

This document provides a description of the country-specific strategy to reach hard-to-reach women in the acceptability study in Belgium, Brazil, Ecuador and Portugal.

3. Overall objectives

This study includes a three-arm prospective acceptability study to:

- assess **attitudes, uptake and users' experiences** related to the use of a HPV self-sampling test (*Obj 1-4*)
- assess the **impact** on looking for follow up care of self-sampling with standard cervical screening strategies (*Obj 5*)
- compare the **feasibility** of an HPV self-sampling in hard-to-reach groups versus educational sessions and standard care (*Obj 6*)

3.1. Study design

A 3-arm prospective acceptability study will be conducted with the following study arms:

Arm 1 – Assessment of screening coverage

Information about the screening coverage rates will be collected, focusing in particular on screening uptake among hard-to-reach women. The screening rates will be collected prior to the start of the study to avoid any contamination, i.e. uptake of screening that may occur through community mobilisation.

Outcome measures that will be examined for arm 1 are:

- Screening coverage at national level
- Screening coverage at local level/in hard-to-reach communities
- Follow-up rate among women who test positive (i.e., have a positive pap smear)

Arm 2 – Information session and follow-up assessment

In arm 2, a community-based researcher will educate women about sexual health and cervical cancer by using the materials that will be developed by the ELEVATE team. Women will be informed about cervical cancer screening (pap smear) and about where they can obtain these services off-site (health facilities); they will receive a contact number to make an appointment as well as information on how to reach the place of the consultation.

Outcome measures that will be examined for arm 2 are:

- Participation rate (i.e., women invited/women who attend the session)
- Knowledge, willingness and uptake of cervical cancer screening prior to the session
- Acceptability of self-sampling
- Uptake of cervical cancer screening through standard services: A 3-month follow-up by phone is proposed to check:

- whether the woman made an appointment; if no appointment was made, we will ask why; if an appointment was made, we will ask if she was able to attend the appointment
- Knowledge of as well as willingness to get screened for cervical cancer screening will also be assessed during the follow-up phone call
- Feasibility

Arm 3 – Information session and self-sampling

A community-based researcher will educate women about sexual health and cervical cancer by using the materials that will be developed by the ELEVATE team. In addition, women will receive information about self-sampling and will be instructed by the community-based researcher on how to take a self-sample using an illustrative cartoon. Women will then be asked to take a sample on-site. The researcher will collect all samples and bring them to the laboratory of UZ Ghent for analysis by an HPV test (yet to be decided which one). Sample analysis is expected to take 2 weeks time. Women who tested positive for HPV will receive a follow-up phone call to notify their result and will again be informed about cervical cancer screening (pap smear) and about where they can obtain these services; they will receive a contact number to make an appointment as well as information on how to reach the place of the consultation.

Outcome measures that will be examined for arm 3 are:

- Participation rate (i.e., women invited/women who attend the session)
- Knowledge, willingness and uptake of cervical cancer screening prior to the session
- Acceptability of self-sampling
- Uptake of the self-sampling test (women who attend the session/women who take the self-sample)
- Attitudes towards self-sampling (reasons to accept/decline the self-sample; advantages and disadvantages versus conventional screening)
- User experiences among those who took a self-sample (easy/difficult; painless/painful; trustworthy/untrustworthy; etc.)
- Uptake of cervical cancer screening through standard services:
 - A 3-month follow up is proposed to check whether the woman made/went to the appointment
- Knowledge of as well as willingness to get screened for cervical cancer screening will also be assessed during the 3 month follow-up phone call
- Feasibility and cost of the intervention

3.2. Specific objectives

Objective 1: Assess and compare **attendance rates** following invitation to participate to the study

Hypothesis 1.1: Attendance will be higher when women are offered self-sampling compared to when women are only offered an educational session.

Objective 2: Evaluate the current **knowledge, willingness and uptake** of cervical cancer screening among participants of the acceptability study (arm 2 & 3); assess knowledge improvement and willingness to get screened 3 months after the intervention

Hypothesis 2.1: Knowledge and willingness to get screened will be poor and uptake of cervical cancer screening among the participants will be lower than the national average (but similar to results found in arm 1)

Hypothesis 2.2: After the information sessions, women will be able to link cervical cancer with HPV and will understand the benefit of screening; willingness to be screened will have increased

Objective 3: Assess **attitudes towards and users' experiences** of the HPV self-sampling test among hard-to-reach women (i.e. participants in arm 3)

Hypothesis 3.1: Attitudes towards on-site HPV self-sampling will be overall positive

Hypothesis 3.2: Women who use the self-sampling tool will have positive users' experiences related to the self-sampling device.

Objective 4: Compare the uptake of the on-site HPV testing (arm3) with the current national screening services (arm1) and with off-site referrals (arm2)

Hypothesis 4.1: Uptake of on-site HPV self-sampling will result in an increase in screening coverage compared to standard practices. (arm 3 vs arm 1)

Hypothesis 4.2: On-site HPV self-sampling will have higher uptake than referrals to off-site screening. (arm 3 vs arm 2)

Hypothesis 4.3: Referral to off-site screening following participation in an educational session on cervical cancer will result in higher screening coverage compared to current practices. (arm 2 vs arm 1)

Hypothesis 4.4: Uptake of off-site screening among those who refuse the self-sampling in arm 3 will be lower than uptake of off-site screening in arm 2

Objective 5: Examine the impact of HPV self-sampling on follow-up testing and care

Hypothesis 5.1: Women whose on-site HPV testing came out positive will go for follow-up testing and care

Objective 6: Assess the **feasibility** of the information session and the self-sampling test

Hypothesis 6.1: Providing cervical cancer screening information and offering on-site HPV self-sampling in hard-to-reach communities will be feasible.

4. Methodology: acceptability study (arm 2 & 3)

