4.1. Study setting/context

Organizations and community-based associations working with socio-economically vulnerable women will be invited to participate. These organizations will be randomly allocated to invite women to either arm 2 or arm 3.

We aim to link the information sessions of the acceptability study to group activities that are offered by the organizations. This was suggested by the community health workers during the focus group discussions as a good way to motivate women to participate. It was reported that it is difficult to gather women for the sole purpose of an information session about their health (especially about cervical cancer that is often not known) and that linking it to an activity for which they are gathered will increase the participation rate.

We are paying attention that organisations and their catchment areas are not too close to each other to avoid spillover.

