4.3. Recruitment of participants

In agreement with the participating organizations, the research team (including the community-based researchers) will hand out invitations (leaflets) to invite women to informative sessions on cervical cancer screening. While handing the invitation, the researcher will shortly describe the goal of the session, emphasizing the benefits for the women. If women are invited for arm 3, they will also be told that they will be offered a self-screening test during the session. Women will receive a leaflet stating the time and place they are expected. Women will be asked to invite other women as well.

We aim to link the sessions to group activities where women are already gathered such as sport activities, integration programs and meals in social restaurants. Therefore, we will work closely with the social

workers and volunteers active in the organizations and will ask for their support to invite women. However, we expect that their contribution will be limited due to their day-to-day workload and tasks.

We will explore with the respective organizations what the best approach is in their context with regard to the timeframe between the invitation and the information session. We learned during the focus group discussions that for many socio-economically vulnerable women it is difficult to commit to show up on another day, for various reasons. Therefore, we aim to organize the educational sessions directly following their group activity, integration class or meal in the restaurant (i.e. the moment they will be invited). In some subgroups of women, such as young mothers, it seems advisable to inform them that they will need to stay a bit longer so they can organize this.

All participants will be offered a small incentive for study participation, such as a voucher.

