4.4. Educational sessions (arm 2 & 3)

Participants included will attend an information session. The information session will take place in the space where the group activities take place (provided by the organizations), the classroom of the integration course or a private room nearby the social restaurants. Sessions will be organized following the group activities (e.g. after sport activity, integration course or meal in social restaurant), with an approximate duration of 20 minutes (excluding sample taking). The sessions will be organized both during weekdays and weekends, depending on the activities they are linked to and according to the preferences of the organizations and women. The content of the session will cover sexual health, cervical cancer and screening services off-site. In the last part of the information session, participants in:

- **arm 2** - will be provided information on how to be screened for cervical cancer and where they can obtain these services off-site.
- **arm 3** - will be provided information on how to be screened for cervical cancer, and where they can obtain these services off-site. In addition, they will receive information on self-sampling and will be offered a self-sampling kit and asked to take a sample on-site and return it.

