5.2.2. Questionnaires

5.2.2.1. *Self-administered questionnaire: knowledge, willingness and uptake of conventional screening (arm 2 and arm 3)*

A self-administered questionnaire will be applied to all participants at the start of each session to assess their current knowledge, willingness to get screened (conventionally) and uptake (*Obj 2*). Through this questionnaire, also socio-demographics, sexual behaviour and pregnancy history will be collected, as well as barriers of accessing cervical cancer screening.

Knowledge will be assessed through verifying whether the participant 1) has heard of cervical cancer, 2) knows the human papillomavirus (HPV) as primary cause, and 3) knows HPV is an STI.

Uptake of conventional screening will be assessed by asking participants' screening history, including 1) lifetime screening, 2) age at first screening and number of pap smears received, and 3) being screened in the last 3 years.

Participants will be asked to indicate their willingness to receive a pap smear and reasons for opting/not opting for conventional screening (reasons for interest/disinterest in continuation among those with previous pap smear uptake). Participants will also be asked to indicate acceptance of self-sampling. (See Appendix I: questionnaire 1)

5.2.2.2. *Self-administered questionnaire: attitudes towards self-sampling (arm 3)*

A self-administered questionnaire will be applied to all participants in arm 3 after the educational session, and before self-sample taking, to assess attitudes regarding self-sampling (pre-intervention) (*Obj 3*).

Attitudes will be assessed through asking participants to use 5-point Likert scale responses to indicate their perceptions of self-sampling and reasons for accepting or not-accepting the self-sample device. (See Appendix II: questionnaire 2)

5.2.2.3. *Self-administered questionnaire: users' perspectives in self-sampling (arm 3)*

A self-administered questionnaire will be applied to all participants in arm 3 who took a self-sample to assess users' experience regarding self-sampling (post-intervention) (*Obj 3*).

Users' perspectives will be assessed through asking participants to use 5-point Likert scale responses report their experience with the self-sampling brush. (See Appendix III: questionnaire 3)

5.2.2.4. *Follow-up questionnaire: knowledge, willingness and uptake of conventional screening (arm 2 and arm 3)*

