6.1. Quantitative data

The primary endpoint is the participation in screening which is defined in Arm 1 as the proportion of women who had a PAP smear taken by a GP or gynaecologist within the national screening program, in Arm 2 as the proportion of women who go for PAP smear after attending the information session with targeted referrals for off-site screening and in Arm 3 as the proportion of women who accept to take an HPV self-test on site after the information session.

Two important measures of take-up will be estimated:

Take-up 1 - To compare the take-up of an on-site HPV screening intervention with the current national screening services accounting for self-selection of women who decide to attend clinics (arm 1 vs. arm 3).

Take-up 2 - To compare the take-up of an on-site HPV screening intervention with targeted referrals to off-site screening (population impact regardless of self-selection) (arm 2 vs. arm 3).

Sample calculation was defined according to an estimated increase in take-up compared with current screening coverage for each study country.

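### Hypothesis 4.4 sets arm 3 women who refuse self-sampling against all arm 2 attendees, so a gap of either sign can come from who refuses and says nothing about the offer

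*Protocol*

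**What the plan says.** Hypothesis 4.4 stands in Protocol section 3.2 under Objective 4 and reads: "Uptake of off-site screening among those who refuse the self-sampling in arm 3 will be lower than uptake of off-site screening in arm 2". Nothing there restricts the arm 2 side. Section 6.1 defines uptake "in Arm 2 as the proportion of women who go for PAP smear after attending the information session with targeted referrals for off-site screening", so the arm 2 denominator is all session attendees.

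Allocation is by organisation (section 4.1): "These organizations will be randomly allocated to invite women to either arm 2 or arm 3". The arm 3 subgroup forms later, at the session, when women "they will receive information on self-sampling and will be offered a self-sampling kit and asked to take a sample on-site and return it" (section 4.4). Arm 3 women know of the test before they decide to attend (section 4.3): "If women are invited for arm 3, they will also be told that they will be offered a self-screening test during the session".

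The eligibility list in section 4.2.1 has no screening-history criterion. Questionnaire 1 (section 5.2.2.1) is given in both arms at the start of the session. It records screening in the last 3 years, and "Participants will also be asked to indicate acceptance of self-sampling". Section 3.1 lists "Acceptability of self-sampling" as an outcome for arm 2 as well as arm 3. For arm 3 it also plans to record "reasons to accept/decline the self-sample; advantages and disadvantages versus conventional screening". The protocol links none of these items to H4.4.

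**The concern.** Refusal of a test is something only arm 3 women can show, and they show it after allocation. Arm 2 contains the counterparts of both the refusers and the acceptors, mixed together. H4.4 therefore compares one kind of woman with a blend of two kinds, and randomisation does not protect that contrast.

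Selection can act either way. Women averse to any screening, or recently screened and not due, would lower off-site uptake among refusers. Women who decline because they prefer a smear taken by a clinician would raise it.

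H4.4 stands beside three between-arm hypotheses, carries a predicted direction and is not marked as descriptive. A lower rate among refusers could be reported as the offer discouraging off-site screening. A higher rate could be reported as reassurance when a real reduction is hidden.

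**Working it through.** The protocol gives no refusal rate, off-site uptake, sample size or error rate for H4.4, so there is no figure to reproduce. The check is a mixture identity. Every numerical input is an assumption.

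**Notation.** a = share of women who would accept a self-test; uA = off-site uptake of would-be acceptors when no self-test is offered; uR = off-site uptake of would-be refusers. Assume that the offer has no effect on refusers and that attendees are alike in both arms.

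- Arm 2 uptake = a·uA + (1 − a)·uR
- Arm 3 refusers' uptake = uR
- Expected gap (refusers minus arm 2) = uR − a·uA − (1 − a)·uR = a·(uR − uA)

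The sign is that of uR − uA, which the documents do not give.

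**Two opposite cases at a = 0.8**

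- uA = 30%, uR = 10%: arm 2 = 0.8 × 30% + 0.2 × 10% = 26%; gap = 10 − 26 = −16 points.
- uA = 10%, uR = 30%: arm 2 = 0.8 × 10% + 0.2 × 30% = 14%; gap = 30 − 14 = +16 points.

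For a between 0.6 and 0.9 the first case gives −12 (0.6 × −20) to −18 (0.9 × −20) points. The second gives +12 to +18.

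**Chance of a significant lower result when the offer does nothing.** This uses a pooled two-proportion z-test at two-sided 5%, ignoring clustering. With nR refusers (rate p1) and n arm 2 women (rate p2), the chance is Φ[((p2 − p1) − 1.96·se0)/se1], where se0 uses the pooled rate and se1 the separate rates. For example, with n = 200, nR = 40, p1 = 0.10 and p2 = 0.26:

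- pooled rate = (4 + 52)/240 = 0.233
- se0 = √(0.233 × 0.767 × (1/40 + 1/200)) = 0.0733
- se1 = √(0.09/40 + 0.1924/200) = 0.0567
- (0.16 − 1.96 × 0.0733)/0.0567 ≈ 0.29, so the chance is about 61%

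Results at a = 0.8, where 100, 200 and 400 women per arm give 20, 40 and 80 refusers:

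| uA | uR | Gap (points) | n = 100 | n = 200 | n = 400 |
|---|---|---|---|---|---|
| 30% | 10% | −16 | 30% | 61% | 93% |
| 30% | 20% | −8 | 9% | 16% | 30% |
| 25% | 25% | 0 | 2.5% | 2.5% | 2.5% |
| 20% | 30% | +8 | 0.5% | 0.2% | 0.1% |
| 10% | 30% | +16 | 0.1% | under 0.1% | under 0.1% |

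The last row shows the masking. Refusers start 16 points above arm 2, so the offer could cut their uptake by up to 16 points (from 30% to 14%) and they would still not fall below arm 2.

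**Like-for-like contrast.** If arm 2 women who would have refused could be identified without error, and attendance were comparable, the expected gap with no effect of the offer is uR − uR = 0, and a significant lower result occurs in 2.5% of trials.

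**Whether the data exist.** Section 4.6 says the Pap smear check at 3 months covers all arm 2 women but, in arm 3, only HPV-positive women. Refusers have no HPV result, so on that text their off-site uptake is not asked. The arm 3 outcomes in section 3.1 and the follow-up questionnaire in section 5.2.2.4 carry no such limit. The sections contradict each other on the arm 3 data that H4.4 needs.

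**The case against.** The strongest reply is that H4.4 makes no causal claim. H4.1 and H4.3 are worded as effects; H4.4 only predicts that one rate will be lower than another. Read as a statement about who declines, 10% against 26% makes it true, not falsely confirmed. This stands: the fault lies in the inference that H4.4 invites, which is why a descriptive label goes most of the way.

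A reader might infer something stronger, that H4.4 would be confirmed whatever the offer does, or is biased toward confirmation. The documents do not support that. It holds only if refusers are less inclined to off-site screening, and no figure says so. The plan to record reasons for declining and views against conventional screening leaves room for women who prefer a clinician's smear, and then the gap reverses.

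It is also fair that H4.4 is not the primary endpoint or either of the two take-up comparisons in section 6.1, and that a statistical analysis plan, not shown here, may add adjustment. But the two groups are fixed by the hypothesis wording. Adjusting for screening history alone would still compare refusers with a mixture.

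Finally, the questionnaire 1 answer is only a proxy for refusal. That also stands, and it is why the contrast proposed below supplements H4.4 and does not replace it as a clean test.

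**Conclusion.** The point holds in this form: H4.4 contrasts a self-selected, post-allocation part of arm 3 with unselected arm 2 attendees, so a difference can arise from selection alone and cannot be read as an effect of the offer. The size is a × (uR − uA): from −18 to +18 points over the assumed settings (a from 0.6 to 0.9, uptakes between 10% and 30%), and zero if refusers and acceptors are equally inclined to off-site screening. All of these inputs are assumptions. The probabilities also ignore clustering and assume that attendees are alike in both arms. The weight is moderate: this is a stated directional hypothesis, but nothing in the protocol ties the primary endpoint or the sample size to it.

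**What to change.** 1. State in H4.4 that comparing refusers with all of arm 2 is descriptive and is not evidence that the offer changes off-site uptake.
2. Add a supportive between-arm comparison of off-site uptake among women who said in questionnaire 1 that they would not accept self-sampling, stratified by or adjusted for screening in the last 3 years. Report how many of these arm 3 women then took a self-sample.
3. Reconcile section 4.6 with sections 3.1 and 5.2.2.4 so that refusers' off-site uptake is recorded at 3 months.

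The cost is the wording of one hypothesis, one subgroup definition and agreement between the follow-up sections. The subgroup items are already planned in questionnaire 1, though its exact wording, in an appendix, should be checked for this use.

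The supportive comparison has limits that should be stated with it:

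- The groups will be small and the intervals wide.
- The answer is given before the session and, in arm 3, after women have been told of the offer.
- Attendance may differ by arm, as Hypothesis 1.1 itself expects.
- Some stated non-acceptors in arm 3 may self-sample after all and then have less reason to seek a Pap smear, which could itself lower their off-site uptake.
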